Most patients also develop a high set-point for feedback inhibition of ACTH secretion by cortisol. In addition to the patient's medical history and physical examination, several laboratory tests and diagnostic techniques are available for the diagnosis of Cushing's disease. Twenty four hour urinary free cortisol (UFC) measurements, blood sampling for serum cortisol levels, and the low-dose dexamethasone suppression test (LDDST) are widely used as screening tests for the diagnosis of Cushing's disease ([Newell-Price et al 1998](#)). To distinguish Cushing's disease from other forms of hypercortisolism, a confirmation of a pituitary source of ACTH secretion is needed. This includes an inappropriately normal or elevated plasma ACTH level and evidence of pituitary tumor on magnetic resonance imaging (MRI) scan or confirmed by bilateral inferior petrosal sinus sampling (BIPSS) after corticotrophin-releasing hormone (CRH) stimulation test (evidence of a pituitary source of ACTH). It is generally accepted that if the ratio of adrenocorticotrophin concentration in the inferior petrosal sinuses to peripheral

blood is greater than or equal to 3.0 after CRH stimulation, a diagnosis of Cushing's disease can be made ([Oldfield et al 1991](#)).

Pituitary resection of the adenoma is the current first-line therapy for Cushing's disease, but surgical failure rates are as high as 25-30% even in the hands of the most experienced neurosurgeons. Additionally postoperative recurrence rates are as high as 20% by 5 years ([Bochicchio 1995](#), [Sonino 1996](#)). Surgery is in many cases complicated by hypopituitarism, which requires complicated life-long hormonal replacement therapy necessary to sustain life. Treatment usually focuses on replacing the target hormones rather than the pituitary hormones, and in patients who have multiple axis deficiencies maintenance with multiple replacement hormones can be difficult, and requiring close and constant medical monitoring, and can be expensive ([Swearingen et al 1999](#)).

Irradiation of the pituitary is another option but it may take many years to be effective and it is curative in only 15 to 45% of the cases. In addition, due to its lack of specificity the procedure also often results in hypopituitarism. Furthermore, there is a 1 to 2% risk of development of secondary tumors in the field of radiation over subsequent years ([Orth 1995](#)).

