3.5.2.12 Concomitant medications including significant non-drug therapies

All concomitant medications and significant non-drug therapies (e.g., surgery, radiation) will be recorded in this study on an ongoing basis. This will also include any information on antidiabetic treatment.

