#### 8.2.1 Secondary efficacy endpoints

The secondary efficacy endpoints are as follows:

---

1. Proportion of patients with a mean UFC  $\leq$  ULN at 1, 3, 6, 12, 24 and 36 months after enrollment into the study.
2. The absolute and percentage change from baseline in biochemical measures of disease activity (mean UFC, serum cortisol, serum cortisol after dexamethasone, salivary cortisol, ACTH, fasting serum lipid profile (total cholesterol, HDL, LDL)) over time.
3. Proportion of patients achieving normalization of biochemical measures of disease activity (serum cortisol, serum cortisol after dexamethasone, salivary cortisol, ACTH) over time, where normalization refers to being within the upper and lower limit of normal ranges.
4. The absolute and percentage change from baseline in clinical signs and symptoms (blood pressure, body weight, body mass index, waist circumference) over time.
5. The proportion of patients with favorable shift from baseline in clinical symptoms of Cushing's disease over time.
6. The change from the last dose of pasireotide s.c. to 90 days after permanent discontinuation of pasireotide s.c. for patients who discontinue pasireotide s.c. prior to completing 3-year observation period. This change will be evaluated for all available continuous efficacy parameters.
7. The absolute and percentage change from baseline in tumor size over time.
8. The absolute and percentage change from baseline in patient reported outcome questionnaires (Cushing QoL and EURO QoL) over time.

All efficacy analyses will be done for all patients in the FAS and for the two cohorts. And all efficacy analyses except those under 5 will be done for the subgroup patients from German sites. Additionally, the efficacy analyses described under 1, 2, and 3 above will be repeated for the following subgroups of patients:

- Patients treated with monotherapy pasireotide s.c. throughout the study
- Patients treated with a combination of pasireotide s.c. with any other therapy for Cushing's disease throughout the study
- Patients who switched from monotherapy to combination therapy or vice versa at any time during the study

For all continuous efficacy variables (biochemical measures of disease activity, blood pressure, body weight, body mass index, waist circumference, tumor size), a Mixed Effects Repeated Measures Model will also be employed to assess the longitudinal changes in these variables.

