Except for the analysis of change from end of treatment to 90 days later, the efficacy analyses will only consider on-treatment values, defined as values assessed before end of treatment + 3 days.

All assessments will be assigned to time windows based on the study day on which the assessment was performed. If there are multiple values within a time window, the assessment closest to the target day of the time window will be used, if not indicated otherwise. Further details including the start and end days of the time windows are available in Appendix 16.1.9 of the CSR.

The continuous efficacy parameters will be also evaluated through a couple of sensitivity analyses: the first will be imputing the worst value at that time window in case of missing data and the second on the patients with the full set of values. The same Mixed Model will be employed for both the analyses.

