The number and percentage of patients who used pasireotide as single therapy, who used it as combination therapy, and who switched from single to combination therapy (or vice versa) will be presented by time period (Day 1 to Day 30, Day 1 to Day 91, Day 1 to 183, etc). Each summary of a time period will only include patients who still received pasireotide s.c. at the end of the time period. Patients will be split up into the three groups based on the following definitions:

- Patients are considered to be on single therapy throughout a period if they did not receive any other medication than pasireotide for Cushing's disease during this period.
- Patients are considered to be on combination therapy throughout a period if they received pasireotide in combination with other medications for Cushing's disease throughout this period. Interruptions of less than 10 days are not considered a switch to single therapy.

---

Study Code: CSOM230B2410

- Patients who switched from single to combination therapy or vice versa are patients who do not fulfill the condition for single therapy and combination therapy throughout the period, as outlined above.
- The frequency of dose changes will be classified as 'no change', 1, 2, 3, >3 changes. Similar classifications will be done for dose increases and dose reductions (including interruptions). The frequencies will be summarized by time window (see Table 6-2 in Section 6.1.7), overall and by reason.

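### Single therapy is defined by medication only, and efficacy values after on-study surgery or irradiation stay in the analyses with no flag or sensitivity analysis

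*SAP*

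**What the plan says.** The only working definitions of single and combination therapy are in SAP 8.3, written for a table of exposure by time period. Single therapy means that patients "did not receive any other medication than pasireotide for Cushing's disease during this period". Patients are on combination therapy "if they received pasireotide in combination with other medications for Cushing's disease throughout this period". Anyone who meets neither condition throughout the period is placed in the switch group.

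SAP 8.2.1 states that "the efficacy analyses described under 1, 2, and 3 above will be repeated for the following subgroups of patients". The first two are "Patients treated with monotherapy pasireotide s.c. throughout the study" and "Patients treated with a combination of pasireotide s.c. with any other therapy for Cushing's disease throughout the study"; the third is patients who switched. No definition or cross-reference is given.

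On which values count, SAP 8.2.1 states that, apart from the 90-day post-treatment comparison, "the efficacy analyses will only consider on-treatment values, defined as values assessed before end of treatment + 3 days". SAP 8.2.1.1 adds that the patient must have been treated during the UFC window and followed to its end. SAP 8.2.1.6 requires the same imaging method as at baseline.

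On collection, protocol 3.5.2.12 states: "All concomitant medications and significant non-drug therapies (e.g., surgery, radiation) will be recorded in this study on an ongoing basis". SAP 4.2.5 lists and summarizes these therapies by cohort in the safety set. SAP 4.2.1 describes prior pituitary surgery and irradiation at baseline.

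**The concern.** There are two separate problems.

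The first is classification. Two programmers could build the efficacy subgroups differently. One who carries over the 8.3 rule puts an irradiated or re-operated patient who takes no other Cushing's drug into monotherapy. One who reads the word therapy in 8.2.1 broadly does not. The monotherapy results for endpoints 1 to 3 depend on which is done.

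The second is attribution, and it remains even if the subgroups are well defined. The secondary objective is to document the efficacy of pasireotide on UFC to Month 36, in a study without a comparator. The protocol introduction says of pituitary irradiation that "it may take many years to be effective and it is curative in only 15 to 45% of the cases". An effect of that kind would tend to appear in the late windows and could not be told apart from a drug effect. A tumor resected on study would be summarized as a change in volume on pasireotide.

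**Working it through.** **Rules that could remove or adjust for a post-procedure value**

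- On-treatment rule (SAP 8.2.1): ends 3 days after end of treatment. SAP 6.1.2 sets end of treatment at the last non-zero dose, so a pause for a procedure followed by resumption leaves later values on treatment. If pasireotide stops for good, values more than 3 days later drop out of these analyses but can enter the 90-day comparison.
- UFC window rule (SAP 8.2.1.1): concerns treatment and follow-up only.
- Tumor volume (SAP 8.2.1.6): concerns imaging method only.
- Mixed model (SAP 6.2.3): terms are window and baseline value only.
- Sensitivity analyses (SAP 8.2.1): worst-value imputation and patients with complete values; both address missing data.

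None of them acts on surgery or irradiation.

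**Which analyses are affected**

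- The therapy subgroups cover endpoints 1 to 3 only, so the definition matters there.
- Tumor size is endpoint 7 and is not split by therapy. Its exposure is in the overall, cohort and German-site analyses.

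**Direction**

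- Endpoint 1 (mean UFC at or below ULN): a successful procedure lowers UFC, so the proportion tends to rise.
- Endpoint 7: resection or irradiation tends to exaggerate shrinkage.
- Endpoint 3: normalization has a lower as well as an upper limit, and SAP 8.2.1.3 requires every measurement in the window to be in range. The protocol introduction says that surgery and irradiation can both cause hypopituitarism. Low ACTH or cortisol counts as not normalized, so the net direction is uncertain.

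**Size for endpoint 1, as an illustration**

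The plan states no figure to reproduce. Inputs:

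- p, response on pasireotide: 14.6% or 26.3% (the two dose groups of the pivotal trial, protocol section 1). These are Month 6 responders without up-titration, so they only approximate the response here.
- c, cure by irradiation: 15% to 45% (protocol section 1), assumed fully reached by Month 36.
- f, share irradiated while on drug: not in the documents; assumed 2% to 20%.
- Independence of drug response and cure is assumed.

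Added proportion = f × c × (1 − p).

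- f = 2%: 0.02 × 0.15 × 0.737 = 0.2 points, up to 0.02 × 0.45 × 0.854 = 0.8 points.
- f = 10%: 0.10 × 0.15 × 0.737 = 1.1 points, up to 0.10 × 0.45 × 0.854 = 3.8 points.
- f = 20%: 0.20 × 0.15 × 0.737 = 2.2 points, up to 0.20 × 0.45 × 0.854 = 7.7 points.

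For scale, the exact 95% intervals are:

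- 15/100: 8.6-23.5%; 26/100: 17.7-35.7%.
- 29/200: 9.9-20.2%; 53/200: 20.5-33.2%.

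The half-widths are about 5 to 9 points. The shift is therefore small against sampling error if few patients are irradiated. At 20% irradiated with the 45% cure rate, it is of similar size.

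**The case against.** The strongest reply is that the 8.3 rule belongs to the exposure table. The efficacy subgroups are named in 8.2.1 with the wider word therapy, and protocol 3.5.2.12 uses that word for surgery and radiation. On that reading an irradiated patient is not monotherapy. This is a fair reading, and a reader should not infer that the SAP has settled on misclassifying these patients. What stands is that 8.2.1 gives no definition, and the only one available says something narrower.

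The study is also exploratory, its primary objective is safety, and it includes combination use by design. Keeping all patients in the overall and cohort analyses is therefore legitimate. That answers a demand to remove them, but not the absence of any analysis showing how much they contribute.

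On-study resection may be uncommon, since enrolled patients had failed surgery or had no surgical option. The planned interval for the median change in tumor volume would barely move with one resected tumor. The mean and the mixed model remain exposed.

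Four stronger readings are tempting but not supported:

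- That monotherapy tumor results are contaminated: no such analysis is planned.
- That the bias always favors pasireotide: this fails for endpoint 3.
- That the procedure data are only listed: SAP 4.2.5 also summarizes them.
- That the effect is large: this needs an affected share that the documents do not give.

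**Conclusion.** The point holds as a gap in definition and in sensitivity analysis. SAP 8.3 and 8.2.1 must be reconciled, because the monotherapy results for endpoints 1 to 3 depend on a definition that 8.2.1 lacks. Independently of that, no rule flags, removes or adjusts for UFC, biochemical or tumor-volume values after on-study surgery or irradiation while pasireotide continues or resumes.

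Upward bias is likely for endpoint 1, as is exaggerated shrinkage for endpoint 7; the direction is open for endpoint 3. The illustrated 0.2 to 7.7 points for endpoint 1 rests on an assumed share of 2% to 20%, full irradiation effect by Month 36, and independence. The protocol's own remark that irradiation may take many years to act suggests that the upper end is generous. Because no hypothesis is tested, the consequence lies in how the long-term efficacy results are read.

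**What to change.** - Use one definition in SAP 8.3 and 8.2.1 under which on-study surgery or irradiation for Cushing's disease counts as other therapy. Monotherapy then means no other medication and no such procedure during the period. State which group a patient joins after a procedure; otherwise the residual rule in 8.3 sends a patient who takes no other Cushing's drug to the switch group.
- Keep the all-patient analyses as planned. Add a sensitivity analysis of endpoints 1 to 3 and 7 that excludes values after on-study pituitary or adrenal surgery or irradiation, and report how many patients and values it removes.
- In SAP 8.2.1.6, summarize tumor volumes measured after on-study pituitary surgery separately from the main summary.
- A split by prior irradiation is optional.

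The cost is SAP wording and programming on data already collected. There will be fewer values in the late windows. The exclusion may also be informative: patients who need a procedure may be poor responders, so removing their later values could itself raise the reported response. Both versions should therefore be shown side by side.

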## 8.4 SAFETY ANALYSIS

Safety and tolerability assessments include AEs, vital signs (blood pressure, heart rate, body temperature), blood glucose (fasting plasma glucose, Hemoglobin A1c), hormones (GH, IGF-1, TSH/free T4), liver enzymes (AST, ALT, alkaline phosphatase,  $\gamma$ GT, total bilirubin), hematology, electrolytes, gallbladder ultrasound and ECGs.

The analyses of safety and tolerability assessments will concentrate on the on-treatment period, defined to be the period from Day 1 to 28 days after last dose of pasireotide s.c. Post-treatment events and assessments (i.e. events and assessments started or performed after the on-treatment period) will be analyzed. In particular, the change between on-treatment period and the period from 28 days after last dose of pasireotide to 90 days after discontinuing pasireotide s.c. treatment will be investigated for continuous parameters in patients who permanently discontinue pasireotide s.c. prior to completing the 3-year observation period.

All safety analyses will be based on the safety set and summarized overall and by cohort. Baseline is described in Section 6.1.6

### 8.4.1 Adverse events (AEs)

All adverse events and the cause of death, as recorded on the completion CRF pages, will be coded using the latest version of the MedDRA coding dictionary that provides the system organ class (SOC) and preferred term (PT) information.

The number and percentage of patients reporting any AE will be summarized by primary SOC and PT. AEs and Serious Adverse Events (SAEs) will be reported and collected from patient's enrollment into the study until 28 days after the last dose of pasireotide s.c. at the patient's last follow-up visit. AEs and SAEs will be collected until 90 days after the last dose for patients who permanently discontinue pasireotide s.c. prior to completing 3 years of treatment.

The primary endpoint of this study is the percentage of patients having any pasireotide s.c.- related AEs and SAEs during the 3-year observation period. Pasireotide s.c.-related AEs are AEs for which the investigator suspected a relationship with pasireotide s.c.

AEs that started or worsened during the on-treatment period are called treatment-emergent AEs.

The incidence of treatment-emergent AEs will be summarized by system organ class (SOC), preferred term (PT) and severity. A patient with multiple occurrences of an AE will be counted only once in the respective AE category.

---

Study Code: CSOM230B2410

The following selection of treatment-emergent AEs will be listed and summarized, overall and by cohort:

- AEs regardless of relationship with pasireotide s.c. (additionally by country). This summary (> 5% in all patients) will also be prepared for the subgroup of patients from German sites
- AEs suspected to be related to pasireotide s.c.
- SAEs regardless of relationship with pasireotide s.c. (additionally by country)
- Deaths
- AEs leading to study drug discontinuation, regardless of relationship with pasireotide s.c. (restricted to patients with primary reason for discontinuation documented as AEs or abnormal laboratory values)
- AEs leading to study drug discontinuation, suspected to be related to pasireotide s.c. (restricted to patients with primary reason for discontinuation documented as AEs or abnormal laboratory values)
- AEs requiring dose adjustment or study-drug interruption, regardless of relationship with pasireotide s.c.
- AEs requiring additional therapy, regardless of relationship with pasireotide s.c.
- Adverse events of special interest, regardless of relationship with pasireotide s.c.

Post-treatment AEs and post-treatment SAEs will be summarized by primary SOC, PT and maximum CTC grade in patients who discontinued pasireotide s.c. prior to completing the 3- year observation period.

In addition, (S)AEs leading to study discontinuation will be listed. Note that there is no respective flag on the eCRF. Therefore the listings will show all (S)AEs which were ongoing at the time of study discontinuation due to AE or which ended the day before.

Also summary on clinically notable AEs (patients who had grade 3/4 AEs, SAEs, AEs leading to discontinuation or other significant AEs) will be prepared for the subgroup of patients from German sites.

Specific groupings of AEs of special interest will be considered and the number of patients with at least one event in each grouping ("category") will be reported. Such groups consist of AEs for which there is a specific clinical interest in connection with pasireotide treatment (i.e. where pasireotide may influence a common mechanism of action responsible for triggering them) or AEs which are similar in nature (although not identical) within project defined group. The specific groupings of AEs as defined in the Attachment 9.2 AESI List (latest documentation available prior to database lock) will be used.

The following tables will be produced:

- AEs of special interest, regardless of relationship with pasireotide s.c., by category, preferred term and maximum CTC grade,
- SAEs of special interest, regardless of relationship with pasireotide s.c., by category, preferred term and maximum CTC grade,
- AEs of special interest, regardless of relationship with pasireotide s.c., by type (any AE, AE suspected to be related to pasireotide s.c., SAE, AE leading to discontinuation, AE requiring dose adjustment or study-drug interruption) and PT

---

Study Code: CSOM230B2410

- AEs of special interest, regardless of relationship with pasireotide s.c., by time interval of onset (0 to < 3 months, 3 to < 6 months, 6 to <9 months, etc.), category and preferred term.

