2.1.1 Endpoint for primary objective

Incidence of pasireotide s.c.-related adverse events and serious adverse events during the 3-year observation period

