3.5.2.1 Adverse events

Information about all adverse events including serious adverse events (SAEs), whether volunteered by the subject, discovered by investigator questioning, or detected through physical examination, laboratory test or other means, must be collected and recorded in the Adverse Event section of the study database (eCRF) irrespective of causal association. The investigator has to include information on all AEs in the individual patient eCRFs. The investigator has to commit to updating this information on a periodic basis but not later than once a month. Information on non-serious AEs is then transferred from the study database to Recordati by PPD data management on a periodic basis but not less frequently than once a month.

All AEs including SAEs occurring in association with exposure to another Recordati drug, if applicable, also have to be notified for recording in the Recordati safety database. Adverse reactions identified for non-Recordati products should be reported to the local Health Authority in accordance with national regulatory requirements for individual case safety reporting or the Marketing Authorization Holder; these will not be recorded in the Recordati safety database.

An adverse event is any undesirable sign, symptom or medical condition occurring on treatment with pasireotide s.c. even if the event is not considered to be related to pasireotide s.c. Medical conditions/diseases present before starting pasireotide s.c. treatment are only considered adverse events if they worsen after starting pasireotide s.c. Abnormal laboratory values or test results constitute adverse events only if they induce clinical signs or symptoms, are considered clinically significant or require therapy, and are recorded in the Adverse Events section. Adverse events will be collected after patients have signed the informed consent or acknowledged an equivalent document (e.g., written information) as per country regulation.

Adverse events will be assessed according to the Common Toxicity Criteria for Adverse Events (CTCAE) version 3.0. If CTCAE grading does not exist for an adverse event (document available upon request), the severity of mild, moderate, severe, and life-threatening, **or** grades 1 - 4, will be used.

In addition, all reports of the following special scenarios are also considered an adverse event irrespective if a clinical event has occurred:

- Drug-drug or drug-food interaction
- Drug use during lactation
- Lack of efficacy

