
Reports of lack of efficacy without an associated clinical event must be recorded on the AE CRF even if lack of efficacy parameters are being collected and recorded elsewhere within the study database.

- Overdose
- Intentional drug abuse and misuse
- Medication errors including drug maladministration
- Dispensing or prescribing errors

Reports of overdose, drug abuse and misuse, drug maladministration and dispensing errors/medication errors without an associated clinical event must be recorded on the AE CRF irrespective of whether or not the information is also being captured on the drug administration record form.

- Drug dependence or addiction
- Withdrawal reaction/syndrome or rebound symptoms
- Unexpected beneficial effect
- Treatment non-compliance (with clinical symptoms)

Note: Occupational or accidental exposure, for example of study personnel or family members of the patient should be reported to the local Health Authority in accordance with national regulatory requirements for individual case safety reporting or Recordati as a spontaneous report.

Any treatment of any adverse event should be recorded on the Adverse Event CRF. Some examples of treatment to be recorded are: no action taken (i.e., further observation only); drug of interest dosage adjusted/temporarily interrupted; drug of interest permanently discontinued due to this adverse event; treatment medication introduced or adjusted; non-drug therapy given; patient hospitalized/patient's hospitalization prolonged.

Once an adverse event is detected, it should be followed until its resolution or until it is judged to be permanent, and assessment should be made at each visit (or more frequently, if necessary) of any changes in severity, the suspected relationship to the drug of interest, the interventions required to treat it, and the outcome.

Information about common adverse effects already known about the medicinal product can be found in the locally available labeling document for the approved indication under evaluation in this study.

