6.5.2.1 Adverse events

The incidence of on-treatment adverse events will be summarized by system organ class and preferred term using the MedDRA dictionary. A similar table will also be produced for the post-treatment period.

Similar summary will also be provided for AESIs summarized by category and preferred term (according to the risks specified in [Section 3.5.2.3](#)).

The primary objective of this study, the number and percentage of patients having any pasireotide s.c.-related adverse event and serious adverse event will also be separately summarized by system organ class and preferred term using the MedDRA dictionary for the on-treatment period.

AE listing will be generated for the overall AEs, pasireotide s.c. related AEs, SAEs, AESIs and deaths. These listings will cover both events that occur during the on-treatment and post-treatment period however, events that occur during the post-treatment period will be flagged.

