## 6 VARIABLES AND ENDPOINTS

### 6.1 DERIVATION RULES

#### 6.1.1 AEs coding/grading

AEs will be graded according to the Common Terminology Criteria for Adverse Events (CTCAE) version 3.0.

If CTCAE grading does not exist for an AE, grades 1 to 4 corresponding to the severity of mild, moderate, severe, and life-threatening will be used. The CTC/severity grade will not be imputed if missing. CTC grade 5 (death) will not be used because the outcome of an AE is not recorded on the AE CRF pages.

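### SAP 8.4.1 limits its death, related-AE, SAE and AESI outputs to treatment-emergent events, while the protocol requires listings that also cover the post-treatment period

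*SAP*

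**What the plan says.** SAP 8.4.1 opens its list of AE outputs with "The following selection of treatment-emergent AEs will be listed and summarized, overall and by cohort". The items that follow include suspected related AEs, SAEs, deaths and AESIs. The same section defines the term: "AEs that started or worsened during the on-treatment period are called treatment-emergent AEs". SAP 8.4 gives the on-treatment period as "defined to be the period from Day 1 to 28 days after last dose of pasireotide s.c".

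For patients who stop pasireotide before three years, SAP 8.4.1 and Protocol 3.5.2 continue AE and SAE collection to 90 days (3 months) after the last dose. For events after the on-treatment period, SAP 8.4.1 plans a summary of AEs and SAEs by system organ class, preferred term and maximum CTC grade in these patients. On grading, SAP 6.1.1 states: "CTC grade 5 (death) will not be used because the outcome of an AE is not recorded on the AE CRF pages".

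Protocol 6.5.2.1 asks for listings of all AEs, related AEs, SAEs, AESIs and deaths. Of their scope it says "These listings will cover both events that occur during the on-treatment and post-treatment period", with the post-treatment events flagged. SAP Section 3, which is the place to declare changes to the planned analysis, declares none.

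**The concern.** This is a post-authorisation safety study whose primary objective is the safety profile. The protocol extends collection beyond 28 days in early discontinuers, counts withdrawal reactions and rebound symptoms as AEs (Protocol 3.5.2.1), and recommends an HbA1c check three months after treatment ends (Protocol 3.5.2.6). Events in that window are therefore of interest by the protocol's own design.

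If SAP 8.4.1 is programmed as written, the listings will be narrower than those the protocol promised, and the change will not have been declared. A reader of the study report could see that a preferred term occurred after treatment. The post-treatment table would not show whether the investigator suspected the drug or whether the patient died of the event.

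**Working it through.** No stated sample size, power or error rate bears on this point, so there is no plan figure to reproduce. The check compares the passages and counts the window.

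**1. Scope of the outputs**

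| Output | Protocol 6.5.2.1 | SAP 8.4.1 |
|---|---|---|
| Listings of AEs, related AEs, SAEs, AESIs, deaths | both periods, post-treatment flagged | treatment-emergent selection |
| Summary of related AEs and SAEs (primary) | on-treatment | treatment-emergent |
| Post-treatment AE summary | yes, by class and term | yes, by class, term and maximum grade |

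The two documents part on the first row. They agree on the second.

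**2. Consistency within the SAP.** SAP 2.2.1 plans a deaths table and listings of deaths, SAEs and AEs for the interim analyses, with no treatment-emergent limit. SAP 4.1 says that the same analysis is done at every time point and that Protocol Section 6 governs. SAP 8.4.1 fits neither statement.

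**3. Three cases in a patient who stops early**

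- *Suspected AE starting on day 40 after the last dose.* It is not treatment-emergent, so it falls outside the related-AE list and table. It is counted in the post-treatment summary, which has no relationship split.
- *Fatal AE starting on day 40.* It is outside the deaths output as headed. In the post-treatment summary its grade can be at most 4.
- *AE starting on treatment, death on day 40.* By onset the AE is treatment-emergent, so the death may enter the deaths output. The SAP does not say whether AE onset or date of death decides.

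The listing of events leading to study discontinuation does not fill the gap. It is keyed to discontinuation due to an AE, and Protocol 3.4.1.1 makes death a separate withdrawal reason.

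**4. Size of the window.** Inputs: on-treatment ends at last dose + 28 days and collection ends at last dose + 90 days (SAP 8.4 and 8.4.1). Days 29 to 90: 90 − 28 = 62 days, and 62/90 = 0.689, or 69% of the post-dose follow-up.

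**5. Scale, as illustration only.** The documents give no discontinuation rate and no event rate. Assume that 30% to 70% of the planned 100 to 200 patients stop early, and that each has a 1% to 5% risk of a related AE or death arising in the window.

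- Patients at risk: 100 × 0.30 = 30, up to 200 × 0.70 = 140.
- Expected affected patients: 30 × 0.01 = 0.3, up to 140 × 0.05 = 7.
- Chance of at least one, 1 − (1 − p)^n: 1 − 0.99^30 = 0.26, up to 1 − 0.95^140 = 0.999.

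The range is too wide to serve as an estimate.

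**The case against.** The strongest reply is that this is a gap in wording. SAP 4.1 imports Protocol Section 6, which contains the flagged listings. SAP 2.2.1 has unrestricted deaths, SAE and AE outputs. SAP 8.4 says that post-treatment events will be analysed. The later AESI tables in 8.4.1, one of which has a suspected-relationship category, state no treatment-emergent limit. The study tests no hypothesis, and 62 days is about 6% of three years (62/1096 = 5.7%).

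Much of this is true. It shows that the SAP contradicts itself, but it does not remove the explicit restriction in 8.4.1. That is the specific AE section, and a programmer would follow it.

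The reply does defeat four stronger readings that a reader might infer:

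- *That a death on day 40 appears in no table or listing.* Treatment-emergent status follows onset or worsening of the AE, so such a death can qualify. SAP 2.2.1 also plans unrestricted deaths outputs, and 8.4.1 codes cause of death from the completion pages.
- *That the primary endpoint should run to 90 days after the last dose.* The endpoint reads "Incidence of pasireotide s.c.-related adverse events and serious adverse events during the 3-year observation period", but Protocol 6.5.2.1 specifies the on-treatment period for that summary. The SAP follows it, and a longer window would create a new conflict.
- *That the reason for not using Grade 5 contradicts the protocol.* Protocol 3.5.2.1 asks for assessment of "the interventions required to treat it, and the outcome" during follow-up. It does not say that outcome is a field on the AE page, and the CRF is not among the documents.
- *That late events go uncollected because of the definition "An adverse event is any undesirable sign, symptom or medical condition occurring on treatment with pasireotide s.c".* The collection windows in Protocol 3.1.1, 3.5.2 and 3.5.2.2 are explicit.

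**Conclusion.** The point holds as a departure from the protocol's listing rule that the SAP does not declare, together with an inconsistency inside the SAP. Post-treatment events are collected and counted. In the 8.4.1 post-treatment summary they lose two attributes: suspected relationship to drug and fatal outcome. The placement of deaths is also undefined.

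The affected window is 62 of 90 post-dose days and applies only to patients who stop early. How many events fall in it cannot be known from the documents. No planned on-treatment figure changes. The conclusion assumes that 8.4.1 would be programmed as worded for the final report; if the team already intends the protocol's listings, the text should say so.

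**What to change.** In SAP 8.4.1:

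- (a) State that the listings of all AEs, related AEs, SAEs, AESIs and deaths cover the on-treatment and post-treatment periods, with post-treatment events flagged.
- (b) Tabulate and list all deaths through the end of follow-up, placed by date of death from the completion page and split on-treatment/post-treatment. The SAP already takes cause of death from that page and uses date of death in 5.1 and 6.1.4; confirm that the page holds the date.
- (c) Add a suspected-relationship split to the post-treatment AE and SAE summary.
- (d) Keep the primary related-AE/SAE table on-treatment, and state that this is the period meant by the endpoint's reference to the 3-year observation period.

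Then bring 2.2.1, 4.1 and 8.4.1 into line, and declare in Section 3 any departure that remains.

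The cost is SAP wording, one flag and a few extra outputs. The AE and SAE data are already collected, and the primary table does not change.
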